### **The specific aims are:**

- 1) To develop SHIM and demonstrate its feasibility. We will develop the SHIM manual, train clinicians and conduct a pilot test with 20 OAT patients with HCV infection at an OAT clinic.
- 3) Using a multi-level implementation science framework, to examine the client, clinician and organizational factors that contribute to SHIM adoption and clinical outcomes.
- 2) To evaluate the effectiveness of SHIM in improving the HCV treatment cascade outcomes using a cluster-randomized three-arm trial design in 480 HCV-infected patients at 12 OAT clinics (4 clinics per arm) randomized to standard of care (N=160) versus SHIM with (N=160) or without (N=160) ECHO facilitation.

## 3 Study Design and Research Methods

### 3.1 Study conditions

#### 3.1.1 Standard of care (SOC)

As of today, HCV diagnostics and treatment is available through the network of specialized infectious diseases clinics. Other clinics (primary care, secondary level or clinics with other specialization) may prescribe and in some cases perform HCV screening, and in case of positive test result provide referrals to the specialized infectious diseases clinics or departments (hepatology centers). Upon admission, physicians are prescribing diagnostic tests to confirm the diagnosis, determine fibrosis stage, and detect possible contraindications. Based on the diagnosis and availability of medications, a treatment regimen is prescribed. Despite the fact that current MoH policy is permitting the use of international clinical guidelines, such as WHO or EASL, in routine practice the number and choice of diagnostic tests and treatment regimens is left to physician's discretion. In most cases, patients are required to have blood biochemistry (liver enzymes), quantitative HCV RNA, genotyping, liver ultrasound, FibroScan, kidney function tests. The cost of diagnostic tests is fully paid by the patients. The choice of treatment regimens usually includes the generic SOF formulations procured by the MoH or regional programs (see Rationale), or other DAA generics that recently became available for purchase at pharmacies. Hepatology center physicians are also prescribing follow-up tests (HCV RNA) to monitor treatment effectiveness.

In this study, the OAT clinics in the SOC arm will be informed of availability of medications at the hepatology centers and instructed to refer patients for screening (to primary care or other clinics, or harm reduction programs) and treatment (to hepatology centers).

### 3.1.2 Simplified HCV integrated model (SHIM)

SHIM will be based on the latest research evidence informing 5 steps to quality HCV treatment in non-specialized care settings [21] and recently approved National Standard on Hepatitis C in adults [22]. The provisional algorithm is presented in Appendix.

#### (1) diagnosis

Majority of the OAT programs in Ukraine already have reasonably high rates of HCV screening (~80% according to our preliminary data), therefore we will enroll patients who have a documented anti-HCV antibody test result. Patients without a documented test result will be referred to receive HCV screening on-site or at a local harm reduction program where it is provided at no cost.

We will evaluate and compare the HCV treatment cascade outcomes starting from HCV diagnosis (HCV RNA test). Where available, a qualitative HCV RNA assay with a lower limit of detection of  $\leq 1,000$  IU/ml will be used to minimize the costs.

#### (2) pretreatment evaluation

SHIM will include the minimum of laboratory tests recommended by the guideline [21], including complete blood count, metabolic panel (creatinine), hepatic function panel, fibrosis score, hepatitis B test. The blood samples, where possible, will be collected at the OAT clinics. APRI or FIB-4 indices will be calculated to determine fibrosis score. Additional ultrasound assessment may be prescribed if APRI or FIB-4 indicate severe fibrosis.

#### (3) simple, once-daily, pan-genotypic HCV treatment regimens

According to the prospective SHIM algorithm, certain conditions (e.g. decreased kidney function, cirrhosis) will trigger a referral to the hepatology center for specialist treatment. In other cases, the OAT physicians will be trained to prescribe the available DAA medications and provide adherence counseling. Given that the OAT patients show up at the clinics daily or on a regular basis, treatment will start as soon as the pre-treatment evaluation is complete. **Given the implementation science premise of this proposal, we will not control which regimens are prescribed by physicians.** On the individual level, the frequency of dispensing may vary depending on the patient's OAT clinic visit schedule, but should not be more frequent than once a week. HIV co-infection (present in almost half of the OAT patients) will be considered an indication for referral to an HIV clinic, but not the hepatology center. HCV treatment in HIV/HCV co-infected patients will be managed by the OAT physician in consultation with the HIV specialist.

#### (4) on-treatment monitoring

The minimized number of clinical assessments will be performed at 4, 8, 12 weeks of treatment. This will include adherence assessment and counseling, side effect assessment, and drug interaction assessment.

#### (5) posttreatment monitoring

HCV RNA PCR to confirm SVR will be performed 12 weeks following completion of therapy. If SVR is not achieved, the patient will be referred to a specialist for re-treatment. Annual HCV RNA testing will be recommended to evaluate for re-infection and liver function tests to monitor other liver conditions.

### 3.1.3 Project ECHO

In this study, for ECHO intervention we will use Zoom videoconferencing that can be accessed on PCs, tablets and smartphones. Participation is linked to continuous medical education (CME), which is required every 2 years for OAT doctors. ECHO meets all of the recommended criteria for CME effectiveness. After a 1-day in-person, comprehensive training session, each bi-weekly / monthly multimedia ECHO session will include a brief didactic training by a national HCV expert (or potential guest speakers from related disciplines like gastroenterology, infectious diseases), followed by a series of cases presented by OAT doctors from their clinics. The ECHO coordinator will seek cases before each session for the specialist to review. “Interactive techniques” emerge from intensive patient-case discussion, where OAT clinicians discuss treatment options and challenges with experts. “Multiple and repeated exposures” to important clinical information is central to ECHO, which focuses repeatedly on evidence-based practices. All video sessions will be recorded and archived for review by providers and participation is monitored centrally through the ECHO hub. If semi-urgent questions arise in between sessions, tele-consults can be sent to the expert and addressed within 24 hours. Tele-consults can then be presented as cases at the next ECHO session. Feedback from prior cases are often discussed briefly to learn about a patient response.

### 3.2 Provision of DAA medications and laboratory tests

To enable on-site medication prescription and dispensing, we will work with the MoH through an established working group to re-route the required number of treatment courses procured by the MoH or regional programs to the OAT clinics.

Due to the centralized procurement (see Rationale), all regions have approximately same ratio of available formulations (with SOF+DAC comprising about 65% in the 2019 procurement). We will ensure that OAT clinics have at least one pan-genotypic regimen available (SOF+DAC or SOF/VEL). **Given the implementation science premise of this proposal, we will not control which regimens are prescribed by physicians.** Available pangenotypic DAA regimens are expected to have comparable effectiveness in our study population [16, 23]. Given that, and assuming even prevalence of genotypes and complicating conditions (e.g. cirrhosis) across the regions, we may safely assume that overall treatment effectiveness will not differ a priori, and the observed differences will result from the study interventions.

Medications will be provided to patients at no cost.

Currently, the diagnostic tests for HCV are provided at a wide range of public and private clinics and laboratories, however these assessments have to be paid for by patients. The average total cost for pre-treatment assessment is about \$100, including the complete blood count, metabolic panel, hepatic function panel, fibrosis staging, INR, but not including elastography. Given the implementation science nature of the proposed research, focusing on real-life outcomes, the costs of laboratory testing will NOT be covered by the project.

For those participants who complete HCV RNA PCR to confirm SVR, HCV RNA PCR for re-infection assessment (12 month after treatment completion) will be recommended. Cost of re-infection assessment will be reimbursed by the project.

### 3.3 Research methods for Aim 1

1) To develop SHIM and demonstrate its feasibility. We will finalize SHIM, train the clinicians and conduct a pilot-test in 10 OAT patients with HCV infection.

We will establish a technical working group on viral hepatitis elimination to finalize SHIM and oversee the study progress. The group will review the latest consensus documents [24], guidelines

(WHO, EASL, AASLD), and the National Standard [22] and produce a localized manual for simplified HCV integrated management model in non-specialty health care institutions.

A systematic training on SHIM for OAT physicians participating in the study will be conducted by the sub-group experts and will cover all parts of the SHIM manual.

Training on research procedures for interviewers and clinical data collectors will occur simultaneously with the intervention training. All research procedures, including participant recruitment (with informed consent), assessment, clinical data collection, etc) will be presented using the Standard Operating Procedures.

Under close supervision of the national experts, we will pilot the manual on a small sample of patients (N=20) at a large OAT site in Lviv. Considering the timeline, the pilot phase will assess HCV care continuum stages up to SVR12. The pilot participants will also undergo all research-related procedures developed for the main phase trial (see the Aim 3 section).

### 3.4 Research methods for Aim 2

3) Using a multi-level implementation science framework, to examine the client, clinician and organizational factors that contribute to SHIM adoption and clinical outcomes.

#### 3.4.1 Approach

For this Aim we use a conceptual framework that serves as a comprehensive heuristic model that may identify different multi-level characteristics that may influence SHIM integration into OAT, including: 1) Client-level factors that may help identify how different subgroups of clients respond to the intervention arms; 2) Provider-level factors that emphasize factors related to the characteristics of the staff, their attitudes toward SHIM and OAT clients with HCV, and fidelity of implementation of SHIM and ECHO; 3) Organizational-level factors that emphasize organizational characteristics of the clinic site (e.g., budget, caseload, size) and more broadly clinical staff attitudes toward change and uptake of SHIM activities. Community-level factors that include local regulations, stigma/discrimination, policing, drug-related policies, institutional response towards incorporating new strategies like SHIM will be assessed based on and controlled for by geographic region. To examine the influence of multi-level factors on implementation of intervention, we will employ a mixed methods approach collecting quantitative and qualitative data to evaluate the influence of client-level, provider-level, organizational, community-level and structural factors that impede or facilitate the implementation of SHIM and effectiveness of study arm interventions. Quantitative data on *changes* in the multi-level factors (client, provider, organization, and community) over time and how they influence the effectiveness of SHIM integration on HCV care cascade (e.g., diagnosis, DAA treatment and retention, SVR) will be compared and contrasted to key themes that emerge from the qualitative data. By merging these data, we may more accurately interpret study findings if one of the intervention arms fails to meet the hypotheses and together these data will inform dissemination strategies to scale-up SHIM more broadly across Ukraine and regionally, where healthcare delivery structures are similar.

#### 3.4.2 Qualitative Assessments

The qualitative data will help us identify the real-world contexts and different organizational, community and structural factors that promote or impede the successful SHIM integration into OAT clinics, which would otherwise be unobserved.

We will conduct two rounds of qualitative assessments during the pilot phase and two rounds in the main phase. The first round will be conducted at the beginning of patient enrolment and the second round at the end of patient follow-up, at the pilot site and each of the 12 sites of the main phase. Each assessment round will include a focus group with randomly selected 6-8 patients and

semi-structured in-depth interviews with clinical staff involved in SHIM implementation, including 1 physician, 1 nurse, and the Chief Administrator. In-depth interviews will also be conducted with participants who haven't started HCV treatment at any stage after receiving positive PCR test for HCV. For the first round of patient focus groups, we will randomly select patients with a positive anti-HCV test result. For the second round, we will select patients who have completed treatment (including testing for SVR12) and several patients (if there are any) who have dropped out of treatment or not completed SVR12 testing. In-depth interviews will also be conducted with participants who have dropped out of treatment or not completed SVR12 testing and was not participating in focus groups. The focus groups and in-depth interviews will be conducted according to the guides that will be modified from the guides that we developed for integrating OAT into primary care [25].

The focus groups and in-depth interviews with clients will elicit feedback on barriers to HCV treatment at the specialized clinics, interactions with clinicians and police, peer norms about HCV, relevance of SHIM (or a theoretical decentralized HCV care model at the SOC sites) and how it could influence their engagement and retention in HCV care, adherence to health recommendations. Interviews with clinicians will elicit their feedback on their perceptions about the relevance of SHIM and ECHO, and perceptions of organizational climate and organizational factors that may facilitate or impede their ability to deliver HCV care. Interviews with clinic administrators will assess their perceptions of organizational factors that may facilitate or impede SHIM integration and ECHO. At the end of follow-up, the patient focus groups will assess whether the HCV treatment became more accessible, what barriers remain, whether any norms and perceptions have changed.

The interviews with clinicians and administrators will assess the actual experience with SHIM, their perception of SHIM sustainability, uptake of HCV diagnosis, treatment and post-treatment monitoring, medication adherence, training and technical assistance using ECHO, as well as their observations about how the integration is proceeding. For the SOC arm, the specific questions about ECHO will be rephrased to ask about theoretical clinical mentoring support.

In all study cities in the main phase, we will additionally recruit for both rounds of in-depth interviews two infectious disease physicians from the hepatology centers. These interviews are aimed to collect information on the existing models of HCV care, attitudes toward PWID and OAT patients and existing barriers and facilitators to HCV diagnosis and treatment. We will also elicit their feedback on the relevance of SHIM, potential weaknesses and strengths of decentralized integrated HCV care provision.

All individual interviews and focus groups will be conducted by trained study staff, at a location identified to assure adequate privacy and confidentiality. Participants will be provided with a separate reimbursement for participation in the individual interview. The interviews will last about one hour, and the focus group up to two hours. The interviews/ focus groups will be digitally recorded and transcribed verbatim for qualitative data analyses by a professional transcription service. 10% of the transcript will be checked by the Co-Investigator responsible for the qualitative component to ensure accurate transcription. All identifying information will be removed from the transcripts, and only the research team and the transcribers will have access to the audio interview data. Audio recordings of interviews will be destroyed after the analyses are complete.

### 3.4.3 Quantitative Assessment of Organizational Factors

During the main phase of the project, OAT site staff and administrators (average N=3 per site) will complete a survey at baseline and the end of follow-up phase. Provider-level Factors will include provider characteristics (e.g., socio-demographics, education and work experience) and their attitudes toward SHIM (or a theoretical integrated HCV care model at the SOC sites) and their

level of self-efficacy implementing SHIM. Attitudes and stigma towards drug users with and without HIV and HCV will be assessed using feeling thermometers operationalized as stereotypical beliefs, attribution beliefs, expectations with regard to rehabilitation chances and social distance [26], and previously used to compare attitudes over time as clinicians gain more contact and experience [27]. For Organizational Factors, clinic administrators will be asked to complete brief surveys on organizational characteristics (number, type, and turnover of staff, types of services provided, hours spent on clinical and administrative tasks, budget). Routine organizational assessments to gauge the progress of implementation and identify areas for future growth are conducted initially by improvement coaches with transfer of implementation to the country team. To understand the organizational changes, we will also have clinic staff and administrators complete several brief validated scales twice annually using REDCap: Organizational Capacity Inventory (e.g., perceived organizational climate, norms, trust and communication) and Organizational Readiness to Change Scale [28] and Organizational Functioning Scale [28]. These brief organizational measures include standardized scales for Social Dominance Orientation [29], which assesses the differences in how staff perceive themselves as “superior” to their patients and often observed in addiction treatment ( $\alpha > 0.90$ ); Resistance Towards Change [30], which assesses how staff respond to innovation within an organization ( $\alpha > 0.90$ ). Discrimination toward OAT patients with HCV by staff will be measured using feeling thermometers [31], which assesses the extent to which staff members believe that individuals should be treated differently for their mental illness (a weakness) and related activities ( $\alpha > 0.85$ ; including subscales) [32], that assesses staff attitudes toward mental illness; as well as additional attitudes that we have created that include information, motivation and necessary skills needed for integration of SHIM into OAT settings and towards provision of HCV services. A review of policies and procedures (and changes) will be used to assess Community-level Factors, including types of services available, geographic proximity of treatment and prevention services, and perceived barriers from patients to accessing services (e.g., hours of service, transportation) from Aim 2. Structural factors will include indicators of policing (i.e. frequency of arrests); incarceration, stigma and discrimination experienced by participants.

### 3.4.4 Analytic plan

Analyses will focus on exploring whether different provider-related or organizational factors influence achieving pre-specified HCV care indicators.

Qualitative data analyses will be conducted on an ongoing basis in coordination with data collection. Thematic coding will be used to analyze the data from the individual interviews based on a grounded theory approach using MAXQDA software system. The Consensual Qualitative Research Method (CQR) will be used by the study team to analyze the data. The CQR method provides a reliable, systematic, and rigorous method in conducting qualitative data analyses - recognizing the importance of context, incorporating an inductive analytic process, using a team and making decisions by consensus, using auditors, and verifying results by systematically checking against the raw data. The key elements of conducting qualitative data analyses using the CQR method include: (1) develop and code domains, (2) construct core ideas, and (3) develop categories to describe consistencies across cases (cross analysis). Key themes related to how different factors may influence the delivery of the intervention will be compared to the quantitative study results for Aim 2 and fidelity of implementation data. Themes that emerge will be put into an organizational matrix to observe changes that occur during integration and participation in ECHO activities.

Some scales may be collinear with each other, therefore principal components will be used to determine which scales should be combined and then either treated as continuous vs ordinal (e.g., high, moderate, low) variables. Bivariate analyses—specifically organizational factors by site—will be conducted to examine trends in the influence of multi-level characteristics on the

implementation and effectiveness of SHIM and ECHO implementation. Analyzing these trends will enable us to address important questions as: “How does organizational readiness to change influence uptake of the HCV care by the staff?” “Are certain subgroups of patients (e.g., younger vs. older) more likely to initiate HCV treatment?” Do changes in stigma (individual, healthcare setting) impact DAA retention or achievement of treatment goals. “Does the doctor/patient relationship influence the HCV care continuum?” “Does OAT patient caseload influence the coverage of SHIM?” Since the study data collection period is 18 months, temporal trends for measures will also be quantitatively described by providing parameters of best fitting parametric models (linear, quadratic/polynomial, exponential) to analyze such questions as: “Do increases in provider confidence lead to greater improvement in HCV cascade indicators?”

In the second part of the analysis, we will examine the role of barriers and facilitators measured using the multi-level framework that includes client-, provider-, organizational-, community-level variables. First, using principal component analysis (PCA), we will identify various dimensions of clinician and organizational behavior that might influence HCV care integration into OAT settings through adoption and implementation of SHIM +/- ECHO at each site, which would summarize the variability in the data. PCA, a transformation used for data reduction, will be applied to multi-level organizational variables. Each principal component represents a different weighted average of the various organizational and client level variables, and each explains a different aspect of the variation observed in patterns of the organization and staff member. Principal components are important ways to group variables that are independent of each other by design, which addresses the issue of multicollinearity [33, 34], which can undermine various modeling strategies. To test the extent to which the barriers and facilitators are associated with higher or even increasing HCV diagnosis, treatment initiation and SVR achievement, we would estimate, using a generalized linear mixed model in which the outcome would be measured at the patient level (level 1), as a dichotomous variable of having been diagnosed/treated/cured or not. Among the covariates in the model, we would include an additional parameter that would incorporate the random effects associated with each provider (level 2), and a random effect associated with each site (level 3), which would be modeled as a function of estimated barrier and facilitator principle components.

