For the secondary outcomes S2b-c, we will collect data using a **paper-based adherence form** administered by clinical personnel during patient visits at treatment initiation, medication pick-up at 4 and 8 weeks, and treatment completion at 12 weeks after initiation. The baseline form will assess self-efficacy and anticipated barriers to treatment adherence for the whole treatment period. The follow-up forms will assess treatment satisfaction, past 30-day and 7-day adherence using visual analog scale [36], side effects, reasons for non-adherence, and reasons for treatment discontinuation (if occurred). At treatment completion, the form will additionally assess the readiness and anticipated barriers to SVR check at 12 weeks after.

For the secondary outcomes S2a and S3a and relevant co-variables, we will collect data using a **patient survey**. The survey will be conducted for the pilot patients and all 3 arms of the main phase at baseline, treatment completion (or 12 weeks after initiation if not completed or 16 weeks after the baseline if not started) and 12 weeks after treatment completion (or 24 weeks after treatment initiation if not completed, or 28 weeks after the baseline if not initiated treatment).

The baseline survey will be administered after confirmation of the diagnosis using HCV RNA test. Patients who will test negative for HCV RNA will be excluded from the following study procedures.

All patient surveys will be collected by an independent interviewer, using study ID via UIPHP REDCap server with clerical checking and patient safeguards described in detail in the human subjects section.

The surveys will include demographics, geospatial assessment, depression (PHQ-9), substance use, alcohol use disorders (AUDIT-C), HIV comorbidity and treatment history, Chronic Liver Disease Questionnaire-Hepatitis C Version (CLDQ-HCV) [37], trust in physician scale [38, 39], HIV risk behaviors, family and social support [40], drug use and mental illness stigma [41], and socio-demographic information.

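### Change in patient-reported stigma is first observed after DAA retention is settled, so the section 3.4.4 question about its impact on retention cannot be read causally

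*Combined protocol and SAP*

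**What the plan says.** Section 3.4.4 lists questions that the Aim 2 trend analyses should answer. One is "Do changes in stigma (individual, healthcare setting) impact DAA retention or achievement of treatment goals". It covers two levels of stigma (patient and healthcare setting) and two kinds of outcome (retention and treatment goals). The section gives no lag, time window or rule on which stigma value may be paired with which outcome.

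**Patient level.** The scale for "drug use and mental illness stigma" is listed among the contents of the patient survey (section 3.5.6). The survey is given "at baseline, treatment completion (or 12 weeks after initiation if not completed or 16 weeks after the baseline if not started"), and once more about 12 weeks after that. Between surveys the only patient form is the adherence form, completed at initiation, "medication pick-up at 4 and 8 weeks, and treatment completion at 12 weeks after initiation". Its content is described thus: "The follow-up forms will assess treatment satisfaction, past 30-day and 7-day adherence using visual analog scale [36], side effects, reasons for non-adherence", and reasons for stopping. No stigma scale is listed.

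**Staff level.** Section 3.4.3 says that site staff and administrators "will complete a survey at baseline and the end of follow-up phase"; this survey holds the attitude and stigma thermometers. The same section has staff fill in several organizational scales twice a year, including Social Dominance Orientation. It then describes discrimination thermometers without giving their timing.

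**Outcomes.** Retention is not defined as an endpoint. The nearest is S1c in section 3.5.5, completion of DAA treatment, which is met when the final prescribed supply has been received. The schedule table in 3.5.6 places dispensing at initiation and at 4 and 8 weeks. SVR12 (P3, section 3.5.4) and the test for it (S1d) come 12 weeks after completion.

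**The concern.** A predictor should be measured before the outcome it is meant to explain. For patient-reported stigma and retention the schedule reverses this: no change score exists until the completion survey, when the patient has already completed or dropped out. Being treated and kept in care may itself lower felt stigma. Regressing retention on the change score cannot separate that from the effect the question asks about. A larger sample sharpens the wrong estimate, and adjusting for arm does not restore the time order.

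For patients who stop or never start, even the date of the second survey is set by the outcome: 12 weeks after initiation, or 16 weeks after baseline.

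Section 3.4.1 says that changes in multi-level factors, and how they influence the cascade including retention, will inform dissemination and scale-up. An association read the wrong way round could therefore end up as advice that reducing stigma keeps patients on treatment.

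**Working it through.** The documents give no figure for this point, so there is none to reproduce. The check sets the schedule beside the outcomes; two illustrations on stated assumptions follow.

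**1. Order of events for a patient, in weeks from initiation of a 12-week course**

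| Event | Source | Week |
|---|---|---|
| Baseline survey, with stigma | 3.5.6 | before 0 |
| Dispensing | 3.5.6, schedule table | 0, 4, 8 |
| Adherence form, no stigma scale listed | 3.5.6 | 0, 4, 8, 12 |
| S1c settled (final supply received) | 3.5.5 with schedule table | 8 |
| Second survey: first change score | 3.5.6 | 12 |
| SVR12 test (S1d, P3) | 3.5.4, 3.5.5 | 24 |

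- Retention: 12 − 8 = 4 weeks after S1c is settled. For a patient whose last supply was collected at week 4 or week 0, the lag is 12 − 4 = 8 or 12 − 0 = 12 weeks.
- If retention is instead read as staying on treatment to week 12, the survey coincides with the outcome and still does not precede it.
- SVR12: 24 − 12 = 12 weeks in the right direction.

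S3a in section 3.5.5 speaks of four interviews while 3.5.6 gives three survey times. Nothing places a fourth during treatment.

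**2. Staff scales given twice a year**

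Assume waves every 26 weeks from week 0 and treatment starts spread uniformly over A weeks. The week-26 wave falls before the end of a 12-week course if the patient starts at week 26 − 12 = 14 or later, so the share is max(0, (A − 14)/A). Measured against the last dispensing at week 8, the cut-off is 26 − 8 = 18 and the share is max(0, (A − 18)/A).

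| A (weeks) | Wave before end of course | Wave before last dispensing |
|---|---|---|
| 14 | 0% | 0% |
| 26 | 12/26 = 46% | 8/26 = 31% |
| 39 | 25/39 = 64% | 21/39 = 54% |
| 52 | 38/52 = 73% | 34/52 = 65% |

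Unless treatment starts are tightly bunched, the twice-yearly scales can precede the outcome for many patients. Measures taken only at baseline and end of follow-up cannot give a change score that does.

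**3. How large a reversed association could be**

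Suppose stigma has no effect on retention, and completing treatment improves stigma by d baseline SDs. With correlation r between the two scores, the SD of the change is √(2(1 − r)). With n₁ non-completers and n₂ completers, SE = SD × √(1/n₁ + 1/n₂), and the chance of two-sided p < 0.05 is about Φ(d/SE − 1.96).

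- 300 starters, 10% non-completion, d = 0.3, r = 0.7: SD = √0.6 = 0.775; SE = 0.775 × √(1/30 + 1/270) = 0.149; 0.3/0.149 = 2.01; Φ(0.05) = 52%.
- Lowest setting (200 starters, 5%, d = 0.2, r = 0.5): SD = 1; SE = √(1/10 + 1/190) = 0.324; Φ(0.62 − 1.96) = 9%.
- Highest setting (300 starters, 20%, d = 0.5, r = 0.7): SE = 0.775 × √(1/60 + 1/240) = 0.112; Φ(4.47 − 1.96) = 99%.

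A separate simulation used 1,000 data sets per setting, with 80% or 90% completing, change score = N(0,1) + d × completion, and a logistic regression of completion on change. For d = 0.2 to 0.5 the median odds ratio was 1.21 to 1.69 per SD. In this set-up the log-odds slope equals d, and exp(0.2) = 1.22 and exp(0.5) = 1.65, which agrees. Rejection was 12–66% with 150 patients and 16–94% with 300, against 4–5% when d = 0.

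**The case against.** The strongest reply is that the protocol specifies no wrong model here. The stigma question is an illustration under bivariate trend analyses described as exploratory. The Aim 2 mixed model has diagnosed, treated and cured as outcomes, not retention, and tests association. Quantitative results will also be compared with qualitative themes. This stands to the extent that nobody can say a false causal effect will be reported. It does not remove the point: the question is worded as impact, names retention, and nothing in 3.4.4 guards against reversed order.

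Three further replies limit the scope, and all three stand.

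- **Staff stigma.** A reader might infer that every stigma measure comes after the outcome for every patient. The documents do not support that. The twice-yearly scales can precede or overlap treatment, and the timing of the discrimination thermometers is not stated.
- **Treatment goals.** For SVR12 testing and SVR12, the change from baseline to the completion survey comes first.
- **Late starters.** A patient surveyed as a non-starter 16 weeks after baseline could begin treatment afterwards, since no rule in the documents prevents it. For that patient the change precedes both initiation and retention.

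Finally, the illustrated error rates are the power to detect an effect of treatment on stigma that was put in by assumption, and they ignore clustering in 12 sites. That is fair. They show that the problem need not be negligible, not how large it will be.

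**Conclusion.** The point holds for patient-reported stigma and DAA retention. On the protocol's own schedule for a 12-week course, the first change score comes about 4 weeks after the last scheduled dispensing, and later relative to the last supply for early dropouts. An association may reflect treatment acting on stigma and cannot support a causal reading.

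At staff level it is certain only for measures confined to the survey at baseline and end of follow-up. It does not apply to S1d or P3.

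The time order rests on the documents, taking S1c as the measure of retention. The size does not: 9% to 99% depends wholly on the assumed numbers of starters, non-completion, score correlation and effect of completion on stigma, none of which the documents give.

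The consequence is confined to one exploratory question. No primary endpoint, Aim 3 arm comparison or sample size depends on it. It still merits correction, because the results are meant to guide scale-up and the remedy uses data already planned.

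**What to change.** Amend section 3.4.4 as follows.

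- Use baseline patient-reported stigma as the predictor of initiation (P2) and completion (S1c).
- Use the change from baseline to the completion survey only for SVR12 testing (S1d) and SVR12 (P3), adjusted for arm and for whether treatment was completed, since completing may move both stigma and these outcomes.
- For staff stigma, use only values measured before the patient's outcome, and state in section 3.4.3 when the discrimination thermometers are given.
- Otherwise report change in stigma as an outcome by arm, or as an association with no causal wording.

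The cost is a change of wording, with no new data collection. The loss is that the exploratory question about change in individual stigma and retention becomes one about baseline stigma.
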